4.2 Handling of deviations in blood collection time points

In this study, the acceptable time deviation in blood sample collection is listed as below. Any sample that is collected outside of the time windows (listed below) should be recorded as a protocol deviation.

Blood Collection Time Window						
Timepoint (h)	Time window	Timepoint (h)	Time window	Timepoint (h)	Time window	
0	Within min pre-dose	30	24 – 72	± 18 min	528 – 1536	± 240 min
2 – 4	± 3 min		96 – 168	± 60 min		
8 – 12	± 6 min		216 – 360	± 120 min		

4.3 Processing of Missing Data

For missing samples before the first quantifiable sample, the concentration values will be treated as “0”. For missing samples between the two quantifiable samples or after the last quantifiable sample, the concentration values will be treated as null listed as either “Not Reportable (NR)” or “No Sample (NS)”. No value will be reported and it will be just represented as “ND” which will be treated as missing data in the table for cases that PK parameters can't be acquired based on the concentration data. Other missing data may occur during safety assessment. Illogical data will be checked.

4.4 Processing of Values below the LLOQ

For samples with concentrations below the lower limit of quantification (LLOQ) will be set to 0 for pharmacokinetic analysis and descriptive statistical analysis.

4.5 Processing of Non-zero Concentration before Dosing

If the pre-dose (0 h) sample provides a quantifiable concentration value, the participants' data can be directly involved in the calculation of pharmacokinetic parameters without correction, but the participants' data will be excluded from PKSS.

5 THE STATISTICAL METHODS

5.1 Participant distribution

Participant disposition will be summarized using the number and percent of Participants according to the following aspects:

- Screened, randomized and treated participants.
- Completion of the trial, withdrawal and reasons for withdrawal.
- Number and percentage of Participant protocol violations or deviations.
- others

All the requirements in the trial protocol must be strictly followed. Any deviation from protocol and regulations in GCP will be defined as protocol deviation. If a deviation is identified, the deviation record should be filled in, and the time of occurrence, process, reason for deviation and measures taken, etc. should be recorded in detail, and the ethics committee and sponsor should be notified. In the data statistics and report, the impact of deviations on the final data and conclusions will be assessed.

When a serious protocol deviation occurs, an assessment should be made. If necessary, the sponsor can terminate this trial early.

5.2 Demographic Data and Baseline Characteristics

Demographic and baseline characteristics will be summarized for all participants included into FAS.

For age, weight, height and BMI: the number of cases, arithmetic mean, standard deviation, median, quartile, min and max will be statistically summarized.

For gender, Ethnicity, race: the cases and percentage will be statistically summarized.

For medical history, surgical history: classification according to MedDRA (Version 27.0 or higher) and the cases and percentage will be statistically summarized.

For smoking/alcohol/allergy/drug abuse history, viral tests, alcohol breath tests and drug abuse tests, antinuclear antibody tests, tuberculosis diagnosis as well as chest X-ray: the cases and percentage will be statistically summarized.

5.3 Medications before Study Drug, Concomitant Medications and Concomitant Non-Drug Therapy Record

Medications before Study Drug, Concomitant Medications and Concomitant Non-Drug Therapy Record will be coded using the World Health Organization (WHO)-Drug, and listed by reported term / preferred term and Anatomical Therapeutic Class classification. Medications before Study Drug, Concomitant Medications and Concomitant Non-Drug Therapy Record taken by participant included into FAS will be listed and statistically summarized with cases and percentage.

5.4 Analysis of PK Parameters

5.4.1 Calculation of PK Parameters

The PK parameters will be estimated based on the actual sampling time with Phoenix

WinNonlin (Certara USA Inc, Version 8.4 or higher) using noncompartmental methods.

Pharmacokinetic parameters to be calculated include:

Parameter	Definition and Calculation
C_{max}	The maximum serum concentration; Observation
AUC_{0-t}	Area under the serum concentration versus time curve calculated to the last measurable observation (C_t); Linear trapezoidal method
$AUC_{0-65days}$	Areas under the serum concentration versus time curve calculated to 65 days postdose; Linear trapezoidal method
$AUC_{0-\infty}$	Area under the serum concentration versus time curve extrapolated to infinity, calculated as $AUC_{0-t} + C_t / K_{el}$
T_{max}	Time to the maximum serum concentration; Observation
K_{el}	Elimination rate constant; calculated as the absolute terminal slope of the log-transformed concentration versus time curve
$t_{1/2}$	Terminal half-life; calculated as $0.693 / K_{el}$
CL/F	Clearance; calculated as Dose / $AUC_{0-\infty}$
V_d/F	Apparent distribution volume; Dose / ($K_{el} \times AUC_{0-\infty}$)

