9 STATISTICAL CONSIDERATIONS

Statistical analysis plan (SAP) should be prepared before statistical analysis. The statistics process should follow SOPs for statistical analysis and related guidance.

If modification of the finalized SAP is necessary, revisions should be clarified together with the sponsor. Revisions and the reasons for revisions will be recorded in the revised SAP. Ensure that the revised SAP be reviewed and approved in accordance with the same procedure as that for the original SAP.

The analysis will be conducted on all participant data after the database is locked.

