9.2.6 Elimination Criteria

The principal investigator, sponsor and statisticians need to work together to decide the participant(s) to be excluded or not from relevant datasets before the statistical analysis. The judgement should be based on the degree of completion of the trial and withdrawal reasons. The relevant notes for data inclusion/exclusion should be recorded. Conditions in which data should be excluded can be as follows (not limited to):

- 1) Data of participants who don't meet the inclusion criteria or meet the exclusion criteria, which may affect the results;

- 2) Data of participants who are incompliant with the clinical protocol during the trial, which should be judged rationally according to the severity of protocol deviations;
- 3) Data of participants with other behavior which may affect pharmacokinetics results during the trial;
- 4) After taking investigational product, the data of individual participants will be excluded from PK similarity analysis (PKSS) on condition that:
 - a. Participants who have positive results of ADA at baseline (0 h);
 - b. The first postdose sample provides C_{max} values;
 - c. The pre-dose (0 h) sample provides a quantifiable concentration value;
 - d. Concomitant medication occur during the trial and there is clear evidence that the combination medication has an effect on the pharmacokinetics (PK) of the investigational products.

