1.5 Blinding and Unblinding

This is a single-blind trial. Only the designated clinical site personnel responsible for drug distribution and administration could reach the randomization code. The personnel and procedure should be blinded as following:

In course of the trial, sponsor staff, investigators in the clinical site and clinical research associates (other than those responsible for drug distribution and administration), statistician (other than unblinded statistician), data managers should be blinded to the treatment assignment. Staff who are responsible for drug distribution and administration should not conduct any protocol-specified safety assessments, e.g. AE or injection site assessments post-dose.

The participants will be blinded to the assigned treatment (T or R) through the dosing process. An eye mask will be put on for participants to avoid viewing the injection.

In addition, the identity of the dosing drug will remain blinded to the bioanalytical staff during sample analysis.

Individual participant treatment assignment should be unblinded in the case of a suspected unexpected serious adverse reaction (SUSAR) that requires knowledge of the study medication received by the participant in order to interpret the event, may be essential for medical management of the participant, and may provide critical safety information about a drug that could have implications for the ongoing conduct of the

trial. Otherwise unblinding is not allowed. Any blinding should be documented and dated. Treatment assignments for individual participants will remain blinded until after the study database has been cleaned and locked.

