2 ASSOCIATED ENDPOINTS

PK Endpoints:

The primary PK endpoints are the maximum serum drug concentration (C_{max}) and areas under the serum concentration versus time curve extrapolated to infinity ($AUC_{0-\infty}$).

The secondary pharmacokinetic endpoints are areas under the serum concentration versus time curve calculated to the last measurable observation (AUC_{0-t}) and to 65 days postdose ($AUC_{0-65days}$), the time to maximum serum concentration (observed) (T_{max}), the elimination half-life ($t_{1/2}$) and terminal elimination rate constant (K_{el}), apparent distribution volume (V_d/F) and clearance (CL/F).

Safety Endpoints

AEs, Serious adverse events (SAEs), vital signs, physical examination, laboratory test, electrocardiogram (ECG), local reactions at the injection site, concomitant therapy, *etc.*

Immunogenicity Endpoints

Incidence and severity of immunogenicity response (ADA/Nab).

3 Analysis Sets

Full Analysis Set (FAS): A dataset of participants who are randomized.

Pharmacokinetic Concentration Set (PKCS): A dataset comprising at least one post-dose effective test component concentration data obtained in participants who receive one dose of the investigational drug. The dataset is for descriptively statistical analysis of the PK concentration data.

Pharmacokinetic Parameter Set (PKPS): A dataset comprising PK parameter data obtained in participants who receive one dose of the investigational drug. The dataset is for descriptively statistical analysis of the PK parameter data.

Pharmacokinetic Similarity Set (PKSS): A dataset comprising data with at least one evaluable PK parameter. This dataset is the main data set for inferring whether the proposed biosimilar product and reference product are PK similar and in this trial. PK parameters of C_{max} and $AUC_{0-\infty}$ will be analyzed. The corresponding period data will not be included in the PKSS, when the conditions occur as following: 1) Participants who have positive results of ADA at baseline (0 h); 2) The first postdose sample provides C_{max} values; 3) The pre-dose (0 h) sample provides a quantifiable concentration value; 4) Concomitant medication occur during the trial and there is clear evidence that the combination medication has an effect on the pharmacokinetics (PK) of the investigational products.

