4.1 Statistical Result Presentation

Conventions for presentation of numerical data:

Listings adopt actual decimals.

In descriptive statistics, Min and Max are kept with the same decimal digits as original data and N is integer.

In descriptive statistics, the arithmetic mean, median, Quartiles (Q1 & Q3), CV%, Geometric Mean, Geometric Mean CV% are kept with one more decimal place than the original data, standard deviation (SD) is kept two more decimal places than the original data. A maximum of four decimal places are kept.

When the number of decimal digits of the original data is inconsistent, the maximum number of decimal digits shall prevail.

Conventions for presentation of PK Parameters:

Values ≥ 0.0001 and < 1 will be reported with 4 decimal places (e.g., 0.0123).

Values ≥ 1 and < 10 will be reported with 3 decimal places (e.g., 1.023).

Values ≥ 10 and < 100 will be reported with 2 decimal places (e.g., 10.23).

Values ≥ 100 and < 1000 will be reported with 1 decimal place (e.g., 100.2).

Values ≥ 1000 or equal to 0 will be reported as a whole integer (e.g., 1000).

Values for T_{max} will be reported with 2 decimal places.

Values for C_{max} will use the decimal retention rule for concentration data.

Elimination Criteria

The principal investigator, sponsor and statisticians need to work together to decide the participant(s) to be excluded or not from the relevant analysis sets before data is unblinded. The judgement should be based on the degree of completion of the trial and withdrawal reasons. The relevant notes for data inclusion/exclusion should be recorded. Conditions in which data should be excluded can be as follows (not limited to):

- 1) Data of participants who don't meet the inclusion criteria or meet the exclusion criteria, which may affect the results;
- 2) Data of participants who are incompliant with the clinical protocol during the trial, which should be judged rationally according to the severity of protocol deviations;
- 3) Data of participants with other behavior which may affect pharmacokinetics results during the trial;

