5.4.4 Sensitivity Analysis

Outlier: Observation extremely discordant with the average level. Outlier may be

caused by the great variability of the variables, or may be an error due to a mistake which can be treated as a missing data however the mistake should be clarified.

Sensitivity Analysis: Sensitivity analyses are a series of analyses conducted against the unexpected conditions, e.g. analysis for data with missing data filled in, subgroup analysis, analysis for a different dataset, adjustment of different covariates, etc. The sensitivity analysis result will be compared with that from the due analysis to explore the robustness of inferences. Sensitivity analysis results can be a supportive data to the main analysis, however, it cannot be the primary rational to make a conclusion.

The sensitivity analysis method is the same as the pharmacokinetic similarity method.

Sensitivity analysis on the outlier or other cases can be conducted, if warranted, during the PK similarity analysis. Influence of outliers can be evaluated by comparing the assessment results in cases with the outliers excluded or not. Reasons should be explained if different conclusions are reached.

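### Does the lack of a stated rule for choosing Kel points and accepting AUC0-∞ leave a co-primary verdict open?

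*SAP*

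**What the plan says.** The trial must place the 90% CI of the geometric mean ratio within 80–125% for both Cmax and AUC0-∞ (SAP 5.4.3). SAP 5.4.1 and Protocol 9.2.1.1 define AUC0-∞ as "Area under the serum concentration versus time curve extrapolated to infinity, calculated as $AUC_{0-t} + C_t / K_{el}$" and Kel as "calculated as the absolute terminal slope of the log-transformed concentration versus time curve", by noncompartmental methods in WinNonlin. The similarity set (PKSS) is "A dataset comprising data with at least one evaluable PK parameter" (SAP section 3), with four listed exclusions, none of which concerns Kel or extrapolation. A parameter that cannot be obtained is shown as ND and treated as missing (SAP 4.3).

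Several provisions govern timing:

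- Under the elimination criteria in SAP 4.1, the investigator, sponsor and statisticians decide which participants are "to be excluded or not from the relevant analysis sets before data is unblinded". They judge on how far each participant completed the trial and why they withdrew, and the list of conditions is open-ended. Protocol 9.2.6 has the same review happen "to be excluded or not from relevant datasets before the statistical analysis".
- The SAP must be final before data lock (SAP section 1).
- "Treatment assignments for individual participants will remain blinded until after the study database has been cleaned and locked" (SAP 1.5).
- "The analysis will be conducted on all participant data after the database is locked" (Protocol 9), with statistical work following standard operating procedures.
- On robustness, "Sensitivity analysis on the outlier or other cases can be conducted, if warranted, during the PK similarity analysis" (SAP 5.4.4). Such results cannot be the main ground for a conclusion.

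**The concern.** A terminal slope can be fitted to the last three points, to the best-fitting window or to every point after the peak. A long extrapolation can be kept or dropped. The text allows all of these, and it does not define what makes a parameter evaluable.

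The gap matters most for truncated profiles. Participants are randomised on Day -1 and dosed once on Day 1, so most people who leave early will still have contributed some samples. If the rule were chosen after lock with treatment codes available, an analyst could in principle prefer the reading that passes. One of the two endpoints that decide similarity would then depend on a choice the plan does not record.

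**Working it through.** **1. The plan's sample size.** Inputs (Protocol 9.8, SAP 1.6): CV 44%, GMR 1.05, limits 0.80–1.25, 90% CI, power 90%, drop-out allowance 15%, N = 238.

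- σ = √ln(1 + 0.44²) = 0.421.
- Evaluable per arm: 238 × 0.85 / 2 ≈ 101. SE = 0.421 × √(2/101) = 0.0592.
- Two one-sided t tests give 89.9% power at 101 per arm, and 202 / 0.85 = 237.6, which rounds up to 238. The plan's figure reproduces.
- With 119 complete profiles per arm, power is 93.8%.

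The plan therefore already allows for the loss of 15% of profiles.

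**2. How much of AUC0-∞ depends on Kel.** Protocol 4.2 gives a half-life of about 2 weeks (336 h), and the last sample is at 1536 h. Then 1536 / 336 = 4.57 half-lives and 2^-4.57 = 0.042. For a one-compartment model with first-order absorption (my assumption), ke = ln 2 / 336 = 0.00206 per h, and the fraction beyond time t is (ka·e^(-ke·t) − ke·e^(-ka·t)) / (ka − ke). At ka = 0.0083 / 0.0145 / 0.025 per h:

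| Last sample | Fraction extrapolated |
|---|---|
| Day 65 (1536 h) | 0.056 / 0.049 / 0.046 |
| Day 23 (528 h) | 0.44 / 0.39 / 0.37 |
| Day 16 (360 h) | 0.62 / 0.55 / 0.52 |

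The choice of slope matters little for a typical completer and a great deal for an early leaver.

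**3. Disagreement between readings.** Assumed: 18 leavers in each arm, 10% assay noise, the three absorption rates above, true GMR 1.05. All readings use post-peak points only. B is the best-fitting window of at least 3 points. C is B plus adjusted R² of at least 0.80. D is C plus at most 20% extrapolated.

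| Exit pattern | B, C and D disagree on AUC0-∞ |
|---|---|
| Even, Day 5–58 | 5.0 / 6.0 / 6.3% |
| Day 8–23 | 8.6 / 10.3 / 10.3% |
| Day 30–58 | 3.2 / 2.4 / 2.2% |

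With 9 leavers per arm, the range over all patterns is 1.4–6.2%.

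B, C and D share one slope and differ only in who is admitted. Varying only the slope among completers (best fit, last 3, all post-peak) changed the verdict in 0.4–0.8% of trials.

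**4. Error rate and power.** At a true ratio of 1.25, each reading alone passes 4.6–5.3%, and at least one of the three passes 5.9–7.6%. Power with even exits is 90.0–92.2% across B, C and D. With Day 8–23 exits it is 86.2–87.7% for B, 89.8–91.2% for C and 89.7–89.9% for D.

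**5. A second simulation with a different model.** It added an assumed LLOQ and, in some scenarios, antibody-accelerated clearance, and it crossed four slope choices with four acceptance rules (500 trials per scenario). Disagreement was 2.0–11.0% varying slope points only, 4.0–9.2% varying acceptance only, and 9–25% over all 16 combinations. With no drop-out it was 3.6%, 3.8% and 15%. At a true ratio of 1.25 (800 trials, base scenario):

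- no acceptance filter: 4.0–4.6% pass;
- fit filter only: 4.1–6.0%;
- 20% extrapolation cap, with or without the fit filter: 7.1–8.6%;
- at least one of the 16: 16.9%.

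Read literally, the plan applies no filter, and that reading keeps the error rate below 5% here.

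**The case for a change.** The strongest case for a change is that the SAP fixes lesser matters (sampling windows, values below the LLOQ, quantifiable pre-dose values) yet leaves the derivation of a co-primary endpoint to the analyst. The review in SAP 4.1 concerns participants. It does not expressly cover slope points, or dropping AUC0-∞ while keeping Cmax. ND has no criterion, and the sensitivity analysis is optional. The 16-combination figures show how far crossed choices can spread, and the second simulation shows that completers are not wholly immune. A few sentences would close the gap.

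The textual part of this stands: no window, fit criterion or extrapolation limit is written anywhere. The inference to a weak test does not follow.

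- Disagreement between rules is not error. Inflation requires several rules to be run and the favourable one kept with codes known. SAP 4.1 takes admission decisions before unblinding, and its completion criterion is aimed at truncated profiles, which drive the disagreement in step 3.
- Protocol 9.2.6 and SAP 4.1 do not conflict. The SAP is the narrower requirement, and meeting it also satisfies the protocol.
- The 15% is a sample-size allowance, not a forecast of when people leave. The 10% figure needs all 36 leavers to go between Day 8 and Day 23, which nothing in the documents suggests.
- Writing in a threshold brings no clear gain. The 20% cap raised the false-pass rate in the second simulation. In the first, with 3 post-peak points and adjusted R² of at least 0.80, 41 / 14 / 6% of accepted Day-16 values still exceeded 1.5 times the true value.
- Dropping AUC0-∞ while keeping Cmax already follows from a PKSS that needs only one evaluable parameter, together with the ND convention.

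**Conclusion.** The concern does not call for a change. The plan omits working detail that a pharmacokinetic analyst supplies from standard noncompartmental practice and the procedures Protocol 9 invokes. The endpoint formula is sound, the sample size reproduces, and admission to the analysis sets is settled blind under the SAP.

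The residual sensitivity is a 2–10% chance that three reasonable admission rules give different AUC0-∞ verdicts. Each of those rules has a false-pass rate of 4.6–5.3%. Power falls more than two points below 90% only for the unfiltered reading with early exits. These figures rest on the assumed half-life, absorption, noise and exit timing, with exits independent of treatment and exposure. They also depend on which readings are counted: crossing slope and acceptance choices gives 9–25%, and a 20% extrapolation cap gave 7.1–8.6% false passes in the second model. Neither result shows that the plan as written misleads, because the unfiltered calculation it states held at 4.0–4.6% in that same model.

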5.4.2 Analysis of PK Parameters

For population included in PKCS, the concentration data of all participants measured for each time point will be used for descriptive statistics, including the number of cases, arithmetic mean, standard deviation, median, quartile, minimum, maximum, geometric mean and coefficient of variation. The individual and mean concentration - time curve (both in linear and semi-log scale) will be plotted. The upper standard deviations at each time point will be presented for the mean concentration – time curve.

For population included in PKPS, descriptive statistics of each PK parameter will be performed. The number of cases, arithmetic mean, standard deviation, median, minimum, maximum, geometric mean, coefficient of variation and coefficient of variation of geometric mean will be calculated for the PK parameters of C_{max} , AUC_{0-t} , $AUC_{0-65days}$, $AUC_{0-\infty}$. The number of cases, arithmetic mean, standard deviation, median, minimum, maximum, geometric mean and coefficient of variations will be calculated for the PK parameters of T_{max} , $t_{1/2}$, K_{el} , V_d/F , and CL/F .

SAS software (version 9.4 or higher) will be used for the statistical analysis.

